9.3.5.1. Primary Efficacy Analyses

The primary endpoint of this study for all tumor types is the confirmed ORR per investigator assessment. The ORR is defined as the proportion of subjects who achieve a confirmed CR or PR according to RECIST v1.1. The ORR of each cohort and its exact 2-sided 90% CI using the Clopper-Pearson method ([Clopper 1934](#)) will be calculated.

For prostate cancer, confirmed PSA response per investigator assessment is another primary endpoint. The confirmed PSA response is defined as a reduction from baseline PSA level of at

least 50%, measured twice ≥ 3 weeks apart. The confirmed PSA response rate and its exact 2-sided 90% CI using the Clopper-Pearson method ([Clopper 1934](#)) will be calculated.

9.3.5.2. Secondary Efficacy Analyses

The DCR will be estimated for each cohort and the 90% CIs will be calculated using the Clopper-Pearson method.

The DOR, PFS, and OS for each cohort, PSA-DOR and PSA-PFS for the prostate cancer cohort will be estimated using the Kaplan-Meier methodology, and the medians and associated 90% CIs will be calculated. Kaplan-Meier plots will be provided as appropriate.

9.3.6. Pharmacokinetic and Immunogenicity Analyses

LV (ADC), total antibody, and MMAE concentrations will be summarized with descriptive statistics at each PK sampling time point. Selected PK parameters for LV, total antibody, and MMAE will be estimated by noncompartmental analysis and summarized using descriptive statistics. These data may be combined with PK data from other clinical trials with LV for population PK and exploratory exposure-response analyses.

The incidence of ATA will be summarized using the safety analysis set.

9.3.7. Biomarker Analyses

Relationships of biomarker parameters (eg, baseline values, absolute and relative changes from baseline) to efficacy, safety, and PK parameters will be explored. Relationships and associated data that are determined to be of interest will be summarized. Details will be described separately in the SAP or Biomarker Analysis Plan.

9.3.8. Safety Analyses

All safety analyses will be performed by cohort and overall using the safety analysis set.

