2. OBJECTIVES

This study will evaluate the efficacy, safety, and pharmacokinetics (PK) of LV in subjects with solid tumors. Specific objectives and corresponding endpoints for the study are summarized in [Table 7](#).

Table 7: Objectives and corresponding endpoints

Primary Objective	Corresponding Primary Endpoint

 Evaluate antitumor activity of LV as monotherapy (Part A, Part B, and Part C Arm 1 [Cohort 8 only]) and in combination with pembrolizumab (Part C Arm 2 and Arm 3, Cohort 8 only) 	
 Investigator-determined confirmed ORR as measured by RECIST v1.1 for all tumor types For prostate cancer, investigator-determined PSA response by Prostate Cancer Clinical Trials Working Group 3 (PCWG3) criteria in addition to ORR
Secondary Objectives	Corresponding Secondary Endpoints

 Evaluate the safety and tolerability of LV as monotherapy (Part A, Part B, and Part C Arm 1 [Cohort 8 only]) and in combination with pembrolizumab (Part C Arm 2 and Arm 3, Cohort 8 only) Evaluate stability and control of disease Evaluate durability of response in subjects who respond to LV as monotherapy (Part A, Part B, and Part C Arm 1 [Cohort 8 only]) and in combination with pembrolizumab (Part C Arm 2 and Arm 3, Cohort 8 only) Evaluate PFS of subjects treated with LV as monotherapy (Part A, Part B, and Part C Arm 1 [Cohort 8 only]) and in combination with pembrolizumab (Part C Arm 2 and Arm 3, Cohort 8 only) Evaluate survival of subjects treated with LV as monotherapy (Part A, Part B, and Part C Arm 1 [Cohort 8 only]) and in combination with pembrolizumab (Part C Arm 2 and Arm 3, Cohort 8 only) Assess PK of LV (Parts A-C) Assess immunogenicity of LV (Parts A-C) 	
 Type, incidence, severity, seriousness, and relatedness of AEs Investigator-determined DCR as measured by RECIST v1.1 Investigator-determined DOR as measured by RECIST v1.1 for all tumors For prostate cancer, investigator-determined PSA-DOR Investigator-determined PFS as measured by RECIST v1.1 for all tumors For prostate cancer, investigator-determined PSA-PFS OS Selected PK parameters for LV, total antibody, and MMAE Incidence of ATAs to LV
Additional Objectives	Corresponding Additional Endpoints

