3. INVESTIGATIONAL PLAN

3.1. Summary of Study Design

This global, open-label, multicenter trial is designed to assess the activity, safety, and tolerability of LV monotherapy for the treatment of solid tumors.

[figure not shown]
Subjects with the following advanced solid tumors will be enrolled:

- Cohort 1: SCLC (Parts A and B)
- Cohort 2: NSCLC-squamous (Parts A and B)
- Cohort 3: NSCLC-nonsquamous (Parts A and B)
- Cohort 4: HNSCC (Parts A and B)
- Cohort 5: esophageal squamous cell carcinoma (esophageal-squamous) (Parts A and B)
- Cohort 6: gastric and gastroesophageal junction (GEJ) adenocarcinoma (Parts A and B)
- Cohort 7: castration-resistant prostate cancer (CRPC) (Part B only)
- Cohort 8: melanoma (Parts B and C)

The study consists of:

- **Part A** (LV q3wk; Cohorts 1 through 6): LV administered by IV infusion at a dose of 2.5 mg/kg on Day 1 of each 21-day cycle (see Section [5.1](#)).
- **Part B** (LV q1wk; Cohorts 1 through 6 will receive 1.0 mg/kg or Cohorts 1 through 8 will receive 1.25 mg/kg; starting with Protocol Amendment 1): LV administered by IV infusion at a dose of 1.0 mg/kg or 1.25 mg/kg on Day 1, Day 8, and Day 15 of each 21-day cycle (see Section [5.1](#)).
- **Part C** (LV 1.5 mg/kg 2q3wk, LV 1.5 mg/kg 2q3wk plus 200 mg pembrolizumab q3wk, LV 1.25 mg/kg q1wk plus 200 mg pembrolizumab q3wk; Cohort 8 only):
 - **Arm 1:** LV administered by IV infusion at a dose of 1.5 mg/kg on Day 1 and Day 8 but not Day 15 of each 21-day cycle as monotherapy.
 - **Arm 2:** LV administered by IV infusion at a dose of 1.5 mg/kg on Day 1 and Day 8 but not Day 15 of each 21-day cycle in combination with 200 mg pembrolizumab administered by IV infusion on Day 1 of each 21-day cycle.
 - **Arm 3:** LV administered by IV infusion at a dose of 1.25 mg/kg on Day 1, Day 8, and Day 15 of each 21-day cycle in combination with 200 mg pembrolizumab administered by IV infusion on Day 1 of each 21-day cycle.

The study design and cohorts for Parts A, B, and C are depicted in [Figure 2](#) and the study schema is depicted in [Figure 3](#).

Figure 2: Study Design and Cohorts – Parts A, B, and C

a Part A will include Cohorts 1 through 6 only.

b In Part B, Cohorts 1 through 6 will receive 1.0 mg/kg LV or Cohorts 1 through 8 will receive 1.25 mg/kg LV (see Section 5.1). The planned LV q1wk doses are 1.0 mg/kg in an initial cohort, to be escalated to 1.25 mg/kg based on safety assessments (details in Section 3.1).

[figure not shown]

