7.6.1.3. Reporting Periods for Adverse Events and Serious Adverse Events

For LV monotherapy (Part A, Part B, Part C Arm 1), the safety reporting period for all AEs and SAEs is from study Day 1 (predose) through the EOT visit or 30 days after the last study treatment, whichever is later. For pembrolizumab and LV combination therapy (Part C Arms 2 and 3), the reporting period for all AEs and SAEs is from study Day 1 (predose) through the EOT visit or 90 days after the last study treatment, whichever is later. However, all study protocol-related AEs are to be recorded from the time of informed consent. All SAEs that occur after the safety reporting period and are considered study treatment-related in the opinion of the investigator should also be reported to the sponsor.

SAEs will be followed until significant changes return to baseline, the event stabilizes (recovering/resolving) or is no longer considered clinically significant by the investigator, or the subject dies or withdraws consent. All non-serious AEs will be followed through the safety reporting period. Certain non-serious AEs of interest may be followed until resolution, return to baseline, or study closure. In particular, these include AEs of peripheral neuropathy in all subjects.

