9. DATA ANALYSIS METHODS

9.1. Determination of Sample Size

Up to approximately 414 subjects may be enrolled in the study, including up to 72 subjects in Part A (q3wk dosing) with each cohort having up to 12 subjects, up to 252 subjects in Part B (q1wk dosing) with each cohort having up to 30 subjects, and approximately 90 subjects in Part C (monotherapy or combination with pembrolizumab) with each arm having 30 subjects.

Additional cohorts may also be added in future protocol amendments for additional indications, alternative dosing schedule, biopsy/biomarker analysis, and LV based combination therapy.

The sample size is not based on power calculations for a formal hypothesis testing but is selected to provide a degree of characterization of commonly occurring AEs in the safety profile and/or a reasonable estimation precision of ORR.

For a sample size of 30 subjects per cohort/arm, assuming confirmed ORR is between 10% and 50%, and confirmed PSA response rate for CRPC is between 10% and 50%, the 2-sided 90% exact confidence interval (CI) are summarized below:

Confirmed ORR*	90% Exact CI (N=30)
10%	(3%, 24%)
20%	(9%, 36%)
30%	(17%, 47%)
40%	(25%, 57%)
50%	(34%, 66%)

*Including confirmed PSA response rate for CRPC cohort

This sample size of 30 subjects per cohort/arm would additionally provide the following probabilities of observing at least 1 patient having an AE, as summarized below.

True AE Incidence Rate	Probability of Observing at Least One Patient Having an AE (N=30)
5%	79%
10%	96%

In Part B, the initial 12 subjects enrolled across the tumor cohorts per dose level will be evaluated for safety after the 12th patient completes the first cycle of treatment. The sample size of 12 allows for a reasonable likelihood of observing a given AE in at least 1 subject even when the incidence of the specific AE is low.

The table below shows the probability of observing an AE in at least 1 subject out of 12 subjects for different underlying incidence of AEs.

Underlying AE Incidence	Probability of Observing the AE in 1 or More Subjects Out of 12 Subjects
1%	11%
5%	46%
10%	72%

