9.3.1.1. Randomization and Blinding

This is an open-label study. Blinding will not be performed. Cohorts in Part A and Part B are single-arm. The cohort in Part C has 3 randomized arms.

For Part C, approximately 90 subjects will be randomized to 1 of the 3 arms with 30 subjects per arm: Arm 1 (monotherapy 2q3wk), Arm 2 (2q3wk combination with pembrolizumab), Arm 3 (q1wk combination with pembrolizumab). The randomization ratio will be 2:1:1 until Arm 1 enrolls 30 subjects. This will ensure that Arm 1 reaches the target enrollment sooner. Thus, of the first 60 subjects, 30 subjects will be enrolled in Arm 1, 15 subjects will be enrolled in Arm 2 and 15 subjects will be enrolled in Arm 3. Afterwards, the remaining subjects will be randomized in a 1:1 ratio to either Arm 2 or Arm 3. Randomization will be stratified according to BRAF mutational status (wild-type versus mutated).

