9.3.8.2. Adverse Events

An overview of AEs will provide a tabulation of the incidence of all AEs, TEAEs, treatment-related AEs, Grade 3 and higher TEAEs, SAEs, treatment-related SAEs, deaths, and AEs leading to study treatment discontinuation. AEs will be defined as treatment emergent if they are newly occurring or worsen following study treatment.

TEAEs will be listed and summarized by Medical Dictionary for Regulatory Activities (MedDRA), preferred term, severity, and relationship to study drug. In the event of multiple occurrences of the same AE with the same preferred term in 1 subject, the AE will be counted once as the occurrence. AEs leading to premature discontinuation of study drug will be summarized and listed in the same manner.

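### Section 9.3.8 gives no arm-level or regimen-level safety summary for Part C, and its cohort and overall columns mix LV alone (AEs to 30 days) with LV plus pembrolizumab (AEs to 90 days)

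*Protocol*

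**What the plan says.** - **Reporting level.** Protocol 9.3.8: "All safety analyses will be performed by cohort and overall using the safety analysis set". Under 9.3.1.7 that set is everyone who received any study drug, with no split by part, arm or regimen.
- **Part C.** Protocol 9.3.1.1: "The cohort in Part C has 3 randomized arms". Each arm has 30 subjects. Arm 1 is LV alone; Arms 2 and 3 add pembrolizumab.
- **AE collection.** Protocol 7.6.1.3 runs monotherapy (Parts A and B, Part C Arm 1) "through the EOT visit or 30 days after the last study treatment, whichever is later", and Arms 2 and 3 "through the EOT visit or 90 days after the last study treatment, whichever is later". Section 7.6 and Appendix D agree. Section 6.1 gives only the 30-day period and makes no exception for Arms 2 and 3.
- **Treatment-emergent events.** Protocol 9.3.8.2: "AEs will be defined as treatment emergent if they are newly occurring or worsen following study treatment". No end date is given.
- **Purpose.** The safety objective in Table 7 covers LV as monotherapy and LV with pembrolizumab. The AE-detection argument in 9.1 is framed by arm as well as cohort: "This sample size of 30 subjects per cohort/arm would additionally provide the following probabilities of observing at least 1 patient having an AE".
- **SAP.** It is written for the Original protocol (section 1), calls the study single arm (5.3) and reports safety by cohort and total (6.6).

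**The concern.** Safety is a secondary objective for two treatments, but the stated rule produces no column that describes either treatment in Part C. The Part C cohort column would combine LV alone with LV plus pembrolizumab. It would also combine planned LV doses of 3.0 mg/kg per cycle (1.5 × 2, Arms 1 and 2) and 3.75 mg/kg per cycle (1.25 × 3, Arm 3), which matters for the exposure summaries in 9.3.8.1. The overall column would add combination subjects to all the monotherapy subjects.

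The collection windows compound this. Because the treatment-emergent definition has no end date, the collection period decides what is counted. Apart from treatment-related SAEs and late end-of-treatment visits, an event on days 31 to 90 can be counted only for a combination subject. Splitting the columns by arm would not cure that. In the one randomised part of the study, Arm 1 and Arms 2 and 3 would still be counted over different periods, and a reader could take a window difference for a drug effect.

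**Working it through.** **1. The plan's own detection figures.** The chance of seeing an event at least once is 1 − (1 − p)^n. At n = 30, 1 − 0.95^30 = 78.5% and 1 − 0.90^30 = 95.8%, matching the stated 79% and 96%. Those figures belong to a column of 30, that is, an arm. The two combination arms together (n = 60) give 95.4% and 99.8%.

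**2. Who is in each column** (planned numbers, protocol 9.1).

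- Monotherapy: 72 (Part A) + 252 (Part B) + 30 (Arm 1) = 354.
- Combination: 30 + 30 = 60. Total 354 + 60 = 414, as stated.
- Combination share of the Part C column: 60/90 = 66.7%.
- Combination share of the overall column: 60/414 = 14.5%.

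**3. Can the regimens be presumed to have equal rates?** The only rates in the documents are the background data in protocol 1.2.4.3 and 1.3.3.2.

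| Event and schedule | LV alone | LV + pembrolizumab |
|---|---|---|
| SAEs, q3wk | 71/191 = 37.2% | 52/91 = 57.1% |
| SAEs, q1wk | 35/81 = 43.2% | 20/45 = 44.4% |
| Sensory neuropathy, q3wk | 69/191 = 36.1% | 37/91 = 40.7% |
| Sensory neuropathy, q1wk (alone: 1.25 mg/kg only) | 28/52 = 53.8% | 7/45 = 15.6% |

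The differences are about +20, +1, +5 and −38 points. With all q1wk monotherapy doses, neuropathy is 36/81 = 44.4%, a difference of −29. The two columns are separate breast-cancer studies, and none of these rates is for the 2q3wk schedule used in Arms 1 and 2. They show that equality cannot be assumed; they do not predict the gap in melanoma.

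**4. Window effect.** The documents give no post-treatment AE rate, so this is an assumption. Let h be a constant monthly rate of first occurrence after day 30, and p the proportion who already have the event by day 30. Days 31 to 90 add (1 − p) × [1 − exp(−h × 60/30.4375)] to incidence in Arms 2 and 3. Multiplying by 60/90 or 60/414 gives the effect on the Part C or overall column. Entries are percentage points for p = 0, then for p = 57.1% (the q3wk combination SAE rate).

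| h per month | Arms 2 and 3 | Part C column | Overall column |
|---|---|---|---|
| 0 | 0; 0 | 0; 0 | 0; 0 |
| 2% | 3.9; 1.7 | 2.6; 1.1 | 0.6; 0.2 |
| 5% | 9.4; 4.0 | 6.3; 2.7 | 1.4; 0.6 |
| 10% | 17.9; 7.7 | 11.9; 5.1 | 2.6; 1.1 |

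The p = 0 entries are ceilings for each h. Deaths before day 90, ignored here, would lower every non-zero entry. For a summary such as any TEAE, where most subjects already have an event, the addition is small.

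**The case against.** **Part C may already be its own unit.** A reader might infer that all of Cohort 8 shares one column, mixing Part B with three Part C arms: four regimens, 60 monotherapy and 60 combination subjects. The documents do not establish this. The synopsis has the primary analysis done separately for cohorts in Parts A, B and C, and 9.3.1.1 treats the Part C cohort as a unit. This stands, so no figure here uses that reading. Part C as its own unit is still two-thirds combination.

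**Arm-level intent is visible.** Table 7 and the cohort/arm sizing suggest that arms were meant to be described. That is a fair inference, and for efficacy it is enough: the same response criteria apply to every arm, and 9.3.5 asks for no overall estimate. For safety it is not enough, because 9.3.8 expressly adds an overall column and the windows differ by regimen.

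**Detail belongs in the SAP.** Protocol 9.3 defers to a SAP to be finalised before database lock, and analysis changes that do not alter site conduct need no amendment. This stands as to where the fix may be made. The SAP supplied does not contain it. That SAP covers the Original protocol, where a single total was sensible, so its wording is out of date rather than wrong.

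**No comparison is planned, and an overall column is only supplementary.** True: there is no formal testing. Adjacent columns from randomised arms will nevertheless be compared. An all-subject column can stay if it is labelled as a supplement.

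**The size is easy to overstate.** This stands. Choosing q3wk for SAEs and q1wk for neuropathy would pick the widest gap each time, and the window ceilings ignore subjects who already have the event.

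**Conclusion.** The point holds on the text alone. Section 9.3.8, followed as written, provides no arm or regimen safety summary for Part C. It produces a cohort column that is 67% combination and an overall column that is 14.5% combination, and it counts events to different times by regimen with no rule to align them. This does not serve a safety objective that covers both monotherapy and combination.

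The size of the distortion cannot be set from the documents. The background rates differ in direction by schedule, and the window effect runs from zero upwards depending on an unknown late-event rate, acting only on subjects still free of the event at day 30. The effect on the overall column is small under every rate tried (at most 2.6 points). The Part C column and the comparison between arms are where it could matter.

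A reader might go further and infer that Part C response rates would be pooled across arms, or that the 6-month analysis trigger is wrong. The documents support neither, and no efficacy or timing error is claimed.

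**What to change.** In 9.3.8 and 9.3.8.2, or in the SAP update for Amendment 04, before database lock:

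1. Summarise Part C safety, including exposure, by randomised arm and separately from Part B Cohort 8.
2. Give two totals, LV monotherapy and LV plus pembrolizumab. Keep an all-subject column only as a labelled supplement.
3. State the AE window used in the main tables, and add one AE summary limited to events starting within 30 days after the last dose of any study treatment, applied to every arm. This aligns the follow-up tail but not time on treatment, so read it beside the exposure summary.
4. Reconcile section 6.1 (30 days, no exception for Arms 2 and 3) with 7.6, 7.6.1.3 and Appendix D.

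The cost is a few sentences and one extra table set from dates already collected, with no new subjects or data. The downside is that arm columns of 30 have wide intervals: by the protocol's own table, an observed 20% carries a 90% interval of 9% to 36%.

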9.3.8.1. Extent of Exposure

Duration of treatment, number of cycles, total dose, and dose intensity will be summarized. Dose modifications, including dose delay, dose reduction, and unplanned dose adjustment, will be summarized. Details will be provided in the SAP.

9.3.8.2. Adverse Events

An overview of AEs will provide a tabulation of the incidence of all AEs, TEAEs, treatment-related AEs, Grade 3 and higher TEAEs, SAEs, treatment-related SAEs, deaths, and AEs leading to study treatment discontinuation. AEs will be defined as treatment emergent if they are newly occurring or worsen following study treatment.

TEAEs will be listed and summarized by Medical Dictionary for Regulatory Activities (MedDRA), preferred term, severity, and relationship to study drug. In the event of multiple occurrences of the same AE with the same preferred term in 1 subject, the AE will be counted once as the occurrence. AEs leading to premature discontinuation of study drug will be summarized and listed in the same manner.

9.3.8.3. Deaths and Serious Adverse Events

SAEs will be listed and summarized in the same manner as all AEs. Events with a fatal outcome will be listed.

9.3.8.4. Clinical Laboratory Results

Summary statistics of laboratory results and changes from baseline will be tabulated by scheduled visit. Grading of laboratory values will be assigned programmatically per the NCI CTCAE v5.0. Shift tables comparing the worst post-baseline to baseline CTCAE grade will be presented. Laboratory values will be listed with grade per CTCAE and flagged when values are outside the normal reference range.

9.3.8.5. Other Safety Analyses

Vital Signs

Vital signs data will be listed. Summary statistics of vital signs and change from baseline may be tabulated where appropriate.

ECOG Status

ECOG status will be summarized for each visit. Shifts from baseline to the best and worst postbaseline score may be tabulated.

9.3.9. Interim Analyses

Interim analysis for futility will be performed separately for each cohort in Part A and Part B after approximately 12 subjects of a given cohort have been treated with a specific LV dose and schedule (LV q3wk at 2.5 mg/kg, LV q1wk at 1.0 mg/kg, or LV q1wk at 1.25 mg/kg [Section 3.1]) and are efficacy evaluable post-baseline. Enrollment to each cohort may be held after approximately 12 subjects for interim futility analysis of the respective cohorts.

The Bayesian predictive probability of success (PPoS) approach will be used to determine the futility criteria (Lee 2008). At the time of each interim analysis, the PPoS will be calculated. PPoS is the probability of achieving “success” should the cohort be continued to the maximum sample size of 30 given the data observed at interim, and a cohort is considered “success” if the posterior probability that the ORR exceeds the response rate of current standard of care (i.e., 15% for SCLC, 10% for NSCLC-squamous, 15% for NSCLC-nonsquamous, 10% for HNSCC, 10% for esophageal-squamous, 15% for gastric and GEJ adenocarcinoma, 10% for melanoma, and 30% for CRPC as referenced in Section 3.1) is greater than 90%.

The ORR observed at interim will be counted as a response for the calculation of PPoS. Table 20 summarizes the PPoS based on the number of responses observed among the first 12 subjects.

Table 20: PPoS based on response among the first 12 subjects

No. of responses ^a among the first 12 subjects	Predictive Probability of Success							
	SCLC (p ₀ =15%)	NSCLC-squamous (p ₀ =10%)	NSCLC-nonsquamous (p ₀ =15%)	HNSCC (p ₀ =10%)	Esophageal-squamous (p ₀ =10%)	Gastric or GEJ adenocarcinoma (p ₀ =15%)	Melanoma (p ₀ =10%)	CRPC (p ₀ =30%)
0	0.05%	0.2%	0.05%	0.2%	0.2%	0.05%	0.2%	0.0007%
1	2%	8%	2%	8%	8%	2%	8%	0.05%
2	16%	36%	16%	36%	36%	16%	36%	0.8%
3	45%	73%	45%	73%	73%	45%	73%	6%
4	77%	94%	77%	94%	94%	77%	94%	21%
5	94%	100%	94%	100%	100%	94%	100%	48%

p₀ is the response rate of current standard of care of each cohort

a Including both confirmed and unconfirmed CR or PR observed at interim

If the PPoS is <10% (i.e., ≤ 1 response among the first 12 subjects, or ≤ 3 responses among the first 12 prostate cancer subjects), the data indicates that it is unlikely the ORR will be better than the response rate of current standard of care at the end of the cohort given interim results and the cohort could be stopped early due to insufficient activity. On the other hand, if the PPoS is >90%, the data suggests that if the same trend continues, there is a high probability to conclude a “success” at the end of the cohort. The PFS and OS will also be evaluated at the time of the interim analysis. Based on the efficacy and safety data, together with the PPoS, a cohort may be stopped early by the sponsor.

The predictive probability method allows the PPoS be computed at any interim time and provides flexibility in monitoring treatment activity continuously after the initial interim analysis.

In addition to the interim analysis for futility, interim data from the study may be presented at scientific meetings such as the annual meetings of the ASCO and the European Society for Medical Oncology.

Continuous monitoring of the benefit-risk profile will be conducted and continuation of enrollment to the cohort may be altered depending on the benefit-risk profile.

